9.3.2. Blinded Procedures

Investigators and research staff will make concerted efforts to withhold all information regarding the assigned treatment from the subject (including family, friends, or caregivers). Subjects will be required to wear an eye mask while the TI or designee is preparing the filler and during the injection.

All evaluations performed by the BLE will be performed separately from the TI

Furthermore, to ensure that they remain blinded and unbiased when making their assessments during the study, the BLE, TI, and the subject will not be allowed to discuss each other's study assessments.

9.3.3. Unblinding Procedures

Unblinding in case of medical emergency is not applicable since the TI, who is in charge of safety follow-up of subjects, will be aware of the treatment administered.

Overall unblinding will take place at the end of the study only after database lock has occurred.

9.4. Pretreatment Procedures and Tests

The procedures and tests to be performed prior to randomization are described for Visit 1 (0 Week).

9.5. Baseline Evaluations and Data Collection

All of the data collected at Visit 1 (0 Week) prior to randomization will be defined as Baseline for the purpose of the study and further analysis.

All evaluations performed by the BLE will be considered as Baseline for the purpose of the primary endpoint analysis.

9.6.1. Study Device

The study device is RHA[®] 3 Please see Section 5.5 and the IB¹⁰ for further information.

9.6.2. Control Device

will be used as the active treatment control for the initial treatment and touch-up treatment, if applicable, in subjects randomly assigned to group. group.

9.6.3. Injection of RHA[®] 3 or

Injection area: The TI will inject each device into the vermillion body, vermillion border, and oral commissures, as needed to achieve optimal aesthetic outcome.

Amount of filler to be administered: Up to 1.5 mL per lip (upper and lower) at each treatment (initial, touch-up, and retreatment).

Information about injection technique, area, and amount of filler will be collected in the eCRF.

Page 78 of 132

	Confidential	
Clinical Investigation Plan		

Confidential Clinical Investigation Plan

10. ADVERSE EVENTS

Subjects will be monitored carefully during the investigation for possible safety events. Safety events include the CTRs, AEs, adverse device effects (ADEs),

All events will be reported and documented on the appropriate eCRF (AE report). Adverse event information will be recorded in the eCRF Adverse Event Form.

All observations and clinical findings, including the nature, seriousness, severity, and relationship to the study or to the control device and/or the procedure, will be assessed by the TI and documented on the eCRF. Documentation will also include a detailed description of the event, treatments rendered in response to the event, and outcomes of the treatment.

Assessment and reporting of safety events will follow all national and local laws and requirements for the conduct of clinical studies, including ISO 14155 and US 21 CFR 812.150.

10.1. Definitions

10.1.1. Adverse Events

An AE is any untoward medical occurrence, unintended disease or injury, or any untoward clinical signs (including an abnormal laboratory finding) in subjects, users, or other persons, whether or not related to the study device, the control device, or the study procedures.

10.1.2. Adverse Device Effects

An ADE is any adverse event related to the use of the study device, the control device, or the study procedures. This definition includes adverse events resulting from insufficient or inadequate instructions for use, deployment, implantation, installation, or operation, or any malfunction of the study or the control device. This definition also includes any event resulting from use error or from intentional misuse of the study or the control device.

10.1.6. Device Malfunction

Device malfunction is a failure of the device to perform in accordance with its intended purpose when used in accordance with the IFU/IB or CIP. A device malfunction may or may not be associated with an AE. If it is, the AE or ADE should be reported separately.

10.2. Evaluation and Assessment

For the purposes of this investigation, any untoward medical occurrence, unintended disease or injury, or any untoward clinical signs that occurs in a subject after randomization is considered an AE, regardless of the investigation group to which the subject is assigned.

Any medical conditions, problems, signs, symptoms, and findings that occur prior to randomization are to be reported as pre-existing conditions. Such conditions should be documented and reported on the medical history eCRF as a pre-existing condition. If a pre-existing condition worsens after randomization (frequency increases and/or severity grade increases), it should be documented as an AE.

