8. INVESTIGATION PROCEDURES

8.1. Procedures by Visit

Subjects must provide written informed consent before any study-related procedures are initiated, including the cessation of prohibited concomitant therapy.

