8.1.1. Visit 1 (0 Week)

Visit 1 is the first day of the study, 0 Week for all subjects.

Eligible subjects seeking lip augmentation will be screened for the study.

The screening procedures will include the following assessments:

- 1. Obtain written informed consent
- 2. Collect demographic information
- 3. Record medical history, including current therapies (e.g., prescription and nonprescription medications) and previous surgeries
- 4. Collect prior and concomitant medications
- 5. UPT for women of childbearing potential
- 7. Both the TI and the BLE perform the TLFS assessment to assess eligibility
- 8. Assess inclusion/exclusion criteria

Signature of the written informed consent, collection of demographics, medical/surgical history, and prior/concomitant medication and washout of prohibited medications (see Section 9.4) may be performed up to 7 days before Visit 1. In any case, signature of the written informed consent must precede all study-related procedures.

Page 55 of 132

Subsequently, the subject will be randomly assigned to RHA[®] 3 or group; for details see Section 9.2.

The TI will **administer the allocated filler** maintaining the blinding described in Section 9.3 and according to the IB and Section 9.6.

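### Protocol 10.2 starts adverse event collection at randomization, so washout-related events that begin earlier and do not worsen are recorded as medical history, contrary to the definitions in 10.1.1 and 10.1.2

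*Protocol*

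**What the plan says.** Four parts of the protocol bear on this point.

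- **Status of washout (8.1).** Written consent is required "before any study-related procedures are initiated, including the cessation of prohibited concomitant therapy". Stopping a prohibited therapy is thus itself a study-related procedure.
- **Timing of washout (8.1.1).** Consent, history taking and "washout of prohibited medications (see Section 9.4) may be performed up to 7 days before Visit 1". Early washout is allowed, not required. Randomization follows the Visit 1 screening steps: "Subsequently, the subject will be randomly assigned to" one of the two groups.
- **General definitions (10.1.1, 10.1.2).** An AE is an untoward occurrence "whether or not related to the study device, the control device, or the study procedures". For device effects: "An ADE is any adverse event related to the use of the study device, the control device, or the study procedures". Neither definition has a start date.
- **Collection rule (10.2).** For this investigation, "any untoward clinical signs that occurs in a subject after randomization is considered an AE". For the earlier period: "Any medical conditions, problems, signs, symptoms, and findings that occur prior to randomization are to be reported as pre-existing conditions". These go on the medical history form. There is one exception: "If a pre-existing condition worsens after randomization (frequency increases and/or severity grade increases), it should be documented as an AE".

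SAP 9 runs all safety analyses on the Safety population, that is, treated subjects. SAP 7.3 summarizes medical history by SOC and PT for the same population. SAP 6.1.7 puts all collected data in listings.

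**The concern.** Take a subject who consents and stops a prohibited medication on day -7 and has an untoward event on day -3. Under 10.1.1 this is an AE. If the investigator thinks the washout caused it, it is also an ADE under 10.1.2. Under 10.2 it is a pre-existing condition. Section 10.2 makes no exception for events that a study procedure may have caused.

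The label has consequences. Protocol 10.2.1 asks for a relatedness judgement for each AE, so an event filed as history gets none. It is left out of the AE and ADE tables in SAP 9.1. For a treated subject it appears instead in the medical history summary, where something the study may have caused reads as background illness. At stake is a complete and correctly labelled record of procedure-related harm during time when the subject has consented and may already have changed medication for the study.

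**Working it through.** The plan gives no figure on this point, so the check is a comparison of texts.

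**Step 1: the window.** It opens with consent and washout, at the earliest 7 days before Visit 1 (8.1.1), and closes at randomization at Visit 1 (8.1.1). Its length is 0 to 7 days per subject. It is 0 for a subject who does everything at Visit 1.

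**Step 2: sort washout-related events by onset and course, and apply both rules.**

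| Event | 10.1.1 / 10.1.2 | 10.2 |
|---|---|---|
| (a) Starts before randomization, then resolves, improves or stays stable | AE, and ADE if related to the procedure | Medical history, not an AE |
| (b) Starts before randomization and worsens afterwards | AE | AE, through the worsening rule |
| (c) Starts after randomization | AE | AE |
| (d) Occurs in a subject who is never randomized | AE | Medical history, not an AE |

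The rules agree on (b) and (c) and disagree on (a) and (d). The gap is those two rows only.

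**Step 3: follow rows (a) and (d) through the SAP.** An event in row (a) in a treated subject appears in the medical history summary (SAP 7.3) and in a listing (SAP 6.1.7), but not in an AE or ADE table (SAP 9.1). In row (d) the subject is outside the Safety population (SAP 5), so no medical history summary applies either. At most a data listing remains.

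**Step 4: effect on the trial's comparisons.** An event before randomization cannot be caused by the assigned device. Adding or omitting such events therefore does not touch the between-arm safety comparison. The primary endpoint, the TLFS change assessed by the blinded evaluator at 12 weeks, does not use AE data.

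**Step 5: look for a rule elsewhere.** Section 8.1.1 refers to 9.4 for washout. The visible text of 9.4 only points back to Visit 1 and contains no safety rule. The visible numbering goes from 10.1.2 to 10.1.6 and from 10.3 to 10.3.4, so intervening sections cannot be read.

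**The case against.** The strongest reply is that 10.1.1 is a generic definition, while 10.2 is written for this investigation and sets its collection window. A site would know which form to use, and the choice of consent or randomization as the starting point is a design preference. This stands in part: 10.2 does tell a site what to do. It does not say that the definitions in 10.1 are narrowed, and it leaves an event that meets the ADE definition without a relatedness assessment.

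A second reply is that a rule for the period between consent and randomization may sit in 10.1.3 to 10.1.5, 10.3.1 to 10.3.3 or the prohibited-medication text, none of which is visible. That cannot be excluded and limits what can be said about reporting. It does not remove the point. The visible rule in 10.2 is categorical, so a hidden rule collecting such events as AEs would contradict it and the two would still need reconciling.

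A third reply is that the exposure is small. Only subjects taking a prohibited medication wash out, early washout is optional, and exclusion criterion 8 removes subjects who need clinically significant continuous treatment within 2 weeks before randomization. This stands, and it is why the point is a modest one. The events are also not lost, since they are recorded as medical history.

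**Conclusion.** The point holds in a narrow form. Protocol 10.2 conflicts with 10.1.1 and 10.1.2 for washout-related events that begin before randomization and do not worsen, and for those in subjects never randomized. Such events are recorded without AE causality assessment or AE tabulation. The window is at most 7 days per subject. How many subjects or events fall in it cannot be derived, because the list of prohibited medications is not visible.

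Three stronger readings are tempting, and the documents do not support them.

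- A reader might infer that harm from washout is left out of the AE count altogether. The worsening rule in 10.2 and the inclusion of any onset after randomization contradict this.
- A reader might infer that serious events would escape safety reporting, more so because 10.5 and 10.6 provide no data monitoring or clinical events committee. This cannot be shown. Sections 10 and 10.3 keep the duties under ISO 14155, 21 CFR 812.150, and FDA and IRB requirements, and part of the reporting text cannot be read.
- A reader might multiply 7 days by the planned enrollment to size the gap. That product does not measure washout exposure, because not every subject washes out or uses the early window.

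The conclusion rests on the visible text of 8.1, 8.1.1, 10.1 and 10.2. It is a low-cost improvement to safety capture and does not threaten the trial's conclusions.

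**What to change.** 1. **Protocol 10.2.** Start AE collection at signature of the informed consent form, at least for events related to study procedures. Limit pre-existing conditions to those present before consent. This brings 10.2 into line with 10.1.1 and 10.1.2.
2. **SAP 9.1.** Add one listing of AEs with onset from consent to first injection, for the Screening population and without attribution to an arm. State that the by-arm tables in the Safety population keep their present scope, events after randomization, so that incidence rates do not change.
3. **SAP 6.1.6.3 and 6.1.7.** Make two conventions explicit for this listing. An AE with missing relationship is now treated as probably related, and a partial start date in the month of injection is set to the injection day. Either rule could move a pre-randomization event into a by-arm table. A yes/no item on the AE form for onset before randomization prevents this.

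The washout itself and every clinical rule stay as they are. The cost is a short amendment to 10.2, one listing, one form item and a few extra AE forms. The small downside is that some unrelated minor events will appear in a pre-treatment listing. If the sections that are not visible already contain a rule for this period, the change reduces to aligning 10.2 with it.

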10.2.1. Relationship to Device

For each AE identified in the investigation, the TI or designee must assess its relationship to the study and the control device and/or to the procedure. The TI must determine whether there is a reasonable possibility that these caused or contributed to an AE.

10.3. Safety Reporting

It is the TI's responsibility to oversee the safety of the investigation at his/her site. This safety monitoring will include careful assessment by the TI and appropriate reporting of all safety events as noted previously.

The site should follow all applicable governance, including FDA regulations, FDA guidance, and IRB requirements for notification of all types of AEs.

Page 85 of 132

Confidential
Clinical Investigation Plan

10.3.4. Device Malfunctions Reporting

Device malfunctions will be reported using the Device malfunction form and supply information relevant to the event.

10.4. Pregnancy

All women of childbearing potential who participate in the study should be counseled on the need to practice adequate birth control and on the importance of avoiding pregnancy during study participation. Women should be instructed to contact the TI or study staff immediately if pregnancy occurs or is suspected.

Pregnancy testing will be conducted prior to administration of the study or the control device on every woman of childbearing potential. A woman who is found to be pregnant at Visit 1 will be excluded from the study and considered to be a screen failure.

A woman who becomes pregnant during the study after the first injection will not receive further injections and will be followed for safety purposes. The assessments scheduled for the Exit visit are required to be performed as soon as possible after learning of the pregnancy.

The TI must report the pregnancy to **pregnancy** within 48 hours of learning of it using the specific pregnancy form and send it to the same e-mail address as for SAE reporting.

10.5. Data Monitoring Committee Not applicable.

Confidential

Clinical Investigation Plan

10.6. Clinical Events Committee

Not applicable.

	Confidential
Clinical Investigation Plan	

11. STATISTICAL METHODS

This section presents a summary of the planned statistical analyses. A statistical analysis plan (SAP) that describes the details of the analyses to be conducted will be written prior to database lock. The SAP will be submitted to the FDA during the course of the study.

11.1. Analysis Populations

The following 4 analysis populations are planned for this investigation:

- Screening: All subjects who provide informed consent and demographic and/or Baseline screening assessment results, regardless of the subject's randomization and treatment status in the investigation.
- Safety: All subjects who receive at least 1 treatment with RHA® 3 or
- Modified intent-to-treat (mITT) analysis set will be used for efficacy analysis. The mITT set is based on the conventional ITT:

	Confidential	
Clinical Investigation Plan		

11.2. Sample Size Determination

The primary endpoint of the study is the difference in the TLFS change from Baseline to 12 weeks after the last day of treatment between subjects treated with RHA[®] 3 and those treated with

11		
		Page 89 of 132

11.3. Subjects and Demographics

11.3.2. Clinical Investigation Plan Deviations

A CIP deviation is any noncompliance with the clinical investigation CIP or International Council for Harmonization of Technical Requirements for Pharmaceuticals for Human Use (ICH) GCP requirements. The noncompliance may be either on the part of the subject, the TI, or study site staff. Corrective actions are to be developed by the site and implemented promptly.

It is the responsibility of the site TI to report any CIP deviations after identification. All deviations must be addressed in study source documents and reported to the sponsor. Clinical investigation plan deviations must be sent to the reviewing IRBs as per local regulations. The site TI is responsible for knowing and adhering to the reviewing IRB requirements. Further details about the handling of CIP deviations will be included in the CIP deviation guidance plan.

Confidential
Clinical Investigation Plan
will be collected
11.4. Effectiveness Analyses Effectiveness analyses will be performed primarily on mITT analysis set.
The primary analysis will be performed as follows: to demonstrate non-inferiority of RHA [®] 3 compared to at 12 weeks after the last treatment; the difference in the change will then be tested between groups (RHA [®] 3 minus

Page 91 of 132

Confider	tial
Clinical Investigation Plan	
Secondary Effectiveness Analysis:	
Secondary analyses will be of descriptive nature	

For the parameters hereafter:

- TLFS: BLE
- Responder rate based on TLFS
- GAIS: BLE,
- FACE-Q scores for each module: Subject (after data standardization, as detailed in SAP)
- Subject satisfaction score: Subject (quantitative scores and categories as described in SAP)

		وجداد والمرا	

For each product, summary statistics (mean, minimum, maximum, SD, and 95% CI of the mean) for the above-mentioned parameters will be provided/presented for each study visit.

For endpoints with qualitative results, frequencies and percentages will be calculated and presented for each study visit.

	Confidential	
Clinical Investigation Plan		
	-	

11.5. Safety Analyses

The TI, through questioning and observations, will report all AEs, their severity and relationship to the study device.

All AEs will be coded using MedDRA. All AEs reported during the study will be described by system organ class and preferred term. The number and percentage of subjects who experience at least 1 AE that are device related (ADEs) will be presented.

Clinical Investigation Plan	Confidential	

```
Confidential
Clinical Investigation Plan
```

12. INVESTIGATOR AND SPONSOR RESPONSIBILITIES

Steps to ensure the accuracy and reliability of data include the selection of qualified TIs and appropriate investigation sites, review of CIP procedures with the TI and associated personnel before the investigation, periodic monitoring visits, and meticulous data management.

12.1. Investigator Responsibilities

The TI is responsible for the conduct of the investigation at the site. **Prior** to shipment of the first study device and first procedure, the TI must do the following:

- Read and understand the CIP
- Sign and complete the Investigator's Agreement
- Provide an accurate financial disclosure and file an update annually and 1 year after the completion of the investigation
- Ensure appropriate IRB and institutional approvals are in place prior to completing any portion of the informed consent process or permitting subject participation
- Complete and file a fully executed clinical trial agreement between sponsor or sponsor's designee, TI, and institution (as applicable)
- Provide assurance of completed training on the study device and procedures being studied under the CIP
- Handle and store the RHA[®] 3 and **Sector** as per the CIP and their respective IFU and IB

	Confidential	
Clinical Investigation Plan		

12.1.1. Deviations From Clinical Investigation Plan

A CIP deviation is defined as an event where the TI or site personnel deviate from the CIP or investigation procedures. It is the TI's responsibility to ensure that there are no deviations from the CIP.

A TI may deviate from the CIP without prior written approval from the sponsor or sponsor's designee in cases of medical emergencies to protect the life or physical well-being of a subject in an emergency. In that event, the TI is required to notify the sponsor and the applicable IRB as soon as possible, but no later than 5 working days after the emergency occurred, of the deviation from the CIP.

12.1.2. Maintaining Records

The TI will maintain the following accurate, complete, and current records relating to the TI's participation in an investigation:

- Correspondence with another TI, an IRB, the sponsor, a monitor, or the FDA.
- · Records of each subject's case history and exposure to the study or control device,

12.1.4. Prohibition of Promotion

The IDE regulations prohibit the promotion of any investigational device. Even though the investigational devices in this investigation have market clearance, they are being investigated in this investigation for a new application. Therefore, no TI (or any person acting on behalf of a TI) may promote the investigational use or represent that the device is safe or effective for the purposes for which it is being investigated, or imply safety or effectiveness (or lack thereof) by discussing individual site experiences in any forum.

Confidential Clinical Investigation Plan

Prohibition of promotion does not apply to promotion of the clinical investigation by the sponsor to facilitate recruitment.

